4.2. Protocol Deviations

All deviations from the protocol are documented in the study file. In addition, deviations are reported to the Institutional Review Board as applicable.

Subject-specific deviations are recorded in the subject's source documents. The Sponsor will review all protocol deviations (PDs) on an ongoing basis and will be responsible for categorizing protocol deviations as exclusionary from IEP. At the time of iDBL and Final DBL, [REDACTED] will download the 'dv' csv file from Zelta including all deviations entered in the system and will send it to the Sponsor. The Sponsor will use this source data to produce a classification Excel file by adding 2 new columns:

- IEPEXCL ("Leads to Exclusion from IEP?"). This column will be filled for each PD with:
 - o 'Yes' if the PD leads to exclusion of the subject from the IEP
 - o 'No' if the PD does not lead to exclusion of the subject from the IEP
- IEPEXCLREAS ("Reason for leading to exclusion from IEP"). This column will be filled for each row where IEPEXCL=Yes, with some categorical reasons of exclusions. Since prohibited medication/vaccine, immunogenicity samples taken out of window, and other major PDs will be recorded as PD and classified as exclusionary from IEP by the Sponsor, only the variable IEPEXCL will be used by [REDACTED] to identify subjects excluded from IEP.

The PD classification file will be finalized prior to iDBL for the Month 1 Analysis, and prior to the final DBL for the Final Analysis.

In addition to the PD classification by the Sponsor, out of window immunogenicity samples will be identified programmatically, and corresponding subjects excluded from the IEP, even if there was not an associated exclusionary PD.

All PDs and their classification will be presented in a data listing.

5. DATA HANDLING

5.1. Computing Environment

All descriptive statistical analyses will be performed using SAS statistical software (Version 9.4), unless otherwise noted. Medical History and adverse events will be coded using Medical Dictionary of Regulatory Activities (MedDRA) version 26.1 unless otherwise noted. Concomitant medications will be coded using B3 World Health Organization (WHO) Drug Global (September 2023) unless otherwise noted.

5.2. Data Conventions

The following conventions will be used:

- **Period definition:**
 - **Screening Period:** The period prior to Day 1 visit.
 - **Treatment and Observation:** The period from date of vaccine administration to Month 1 visit (included).
 - **Follow-up:** The period from Month 1 visit (excluded) to Month 6 visit.
- **Visits:**
 - **Study day 1:** The date of study vaccine administration.
 - **End of Treatment Visit:** The Month 1 visit, or the early discontinuation visit for subjects who withdraw study prior to Month 1 visit.
 - **End of Study Visit:** The last recorded visit date.
 - **Unscheduled visits:** Unscheduled visits results will be listed, but not included in tables or graphs. Rules to map unscheduled visit to analysis visit are defined in Section 5.5.
- **Baseline characteristics and change from baseline:**
 - Weight values recorded in pounds will be converted to kilograms using the following formula: kilograms = pounds/2.2046.
 - Height values recorded in inches will be converted to centimeters using the following formula: centimeters = inches*2.54.
 - Duration on study (weeks) = (Last visit date – randomization date + 1) / 7.
 - (Absolute) Change from baseline = Value at the time point – Baseline value.
- **Adverse events:**
 - **Solicited Adverse Events** will be analyzed using the nominal visit (i.e. the page) on which they were recorded and not according to the date they were entered.

- **Solicited Adverse Events continuing beyond 7 days:** Solicited AEs continuing beyond 7 days will be reported in the “Adverse Events (Unsolicited)” page as per Case Report Form (CRF) Completion guidelines and will be identified programmatically as all unsolicited adverse events with answer ‘Yes’ to the question ‘Is this a Prolonged Solicited Adverse Event?’. The corresponding question in the diary page (‘Were any of the above symptoms continuing after Day 7?’) will not be used as it is expected that both sources will be reconciled before iDBL so that only the unsolicited page can be used for the analysis.
- **Immunogenicity:**
 - OPA results are reported as titer and IgG results are reported as concentration
 - **GMC [or GMT]:** The geometric mean concentration (or titer) = antilog10 (LSMeans [$\log_{10} x$]), where x is the assay result and LSMeans is the least square means calculated by the model.
 - **GMR:** The geometric mean ratio = antilog10 (LSMeans [$\log_{10} x$]) / antilog10 (LSMeans [$\log_{10} y$]), where x and y are the 2 assays results and LSMeans is the least square means calculated by the model.
 - **Fold Ratio:** The ratio between titer/concentration at Month 1 visit and the one at Day 1.
 - **GMFR:** The geometric mean fold ratio = antilog10 (LSMeans [$\log_{10} y$]), where y is the assay fold ratio and LSMeans is the least square means calculated by the model.
 - **4-fold increase:** A subject achieved 4-fold increase if fold ratio ≥ 4
 - **BLQ:** Below lower limit of quantification (LLOQ). Per Center for Biologics Evaluation and Research (CBER) criterion, BLQ titer/concentration will be analyzed as:
 - 0.5*LLOQ for calculations of GMT/GMC and GMT/GMC Ratios (GMRs)
 - 1*LLOQ for calculations of fold ratio.
 - **ULOQ:** Upper limit of quantification. Titer/Concentration above ULOQ will be analyzed as:
 - 1*ULOQ for all calculations (GMT/GMC, GMRs, fold-ratio)

5.3. Methods of Pooling Data

Not Applicable.

5.4. Withdrawals, Dropouts, Loss to Follow-up

Subjects who undergo Early Discontinuation after randomization and before Day 1 vaccine administration may be replaced by randomizing an additional subject at the Sponsor’s discretion. Subjects who undergo Early Discontinuation after study vaccination will not be replaced.

6. STATISTICAL METHODS

6.1. Sample Size Justification

For subjects enrolled in Stage 1 of the study, comprising 64 subjects 50 to 64 years of age, sample size is not driven by statistical assumptions for formal hypothesis testing but is based on the safety objective for the study. With 16 subjects, events that occur at a frequency of 15% or more will be detected with at least 92% probability and events that occur at a frequency of 10% or more will be detected with 81% probability. Therefore 16 subjects in each treatment group are proposed as the basis for the number of subjects in whom to conduct the first safety assessment.

For subjects enrolled in Stage 2 of the study, comprising approximately 736 subjects aged 50 to 64 years as well as a minimum of 200 subjects aged 65 years and older, sample size is not based on statistical justification. A total of approximately 800 subjects aged 50 to 64 (with a minimum of 200 subjects aged 60 to 64), as well as a minimum of 200 subjects aged 65 years and older, should provide sufficient information to assess safety and immunogenicity in the older age groups. The sample size will also be adequate to plan future studies.

6.2. General Statistical Methods

6.2.1. General Methods

All outputs will be incorporated into Microsoft Word files, sorted, and labeled according to the International Conference on Harmonization (ICH) recommendations, and formatted to the appropriate page size(s).

Tabulations will be produced for appropriate demographic, baseline, safety, and immunogenicity parameters. For categorical variables, summary tabulations of the number and percentage within each category (with the number of subjects with missing data) of the parameter will be presented. For continuous variables, the mean, median, standard deviation, minimum and maximum values will be presented.

Statistical hypothesis testing will be performed on immunogenicity parameters with all tests conducted at the 2-sided, 0.05 level of significance. Summary statistics will be presented, as well as 95% confidence intervals (CI) on selected parameters, as described in the sections below.

6.2.2. Definition of Baseline

For the following endpoints, baseline is defined as the assessment collected the closest to the study vaccine administration on Day 1 or prior to study vaccine administration (up to 30 days before Day 1):

- Laboratory Parameters
- Immunogenicity

Laboratory and immunogenicity results from samples collected on Day 1 after the vaccine injection can still be considered as baseline results.

For the following endpoint, baseline is defined as the last non-missing assessment prior to study vaccine administration:

- Vital signs: Day 1 prior to study vaccine administration (up to 30 days before Day 1)

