## Study Design

This Phase 1/2 parallel-group, randomized, 2 stage observer-blind study is to be conducted in 3 populations of healthy adults, aged 50 to 59, 60 to 64, and 65 years and older. Subjects will be randomly assigned in a 1:1:1:1 ratio to receive either VAX-31 at 1 of 3 dose levels or a single dose of PCV20, the active comparator.

In Stage 1 of the study, 64 subjects (16 for each VAX-31 dose group and 16 for the comparator group) 50 to 64 years of age will be enrolled initially. In Stage 2, approximately 736 additional adults aged 50 to 64 years as well as a minimum of 200 adults aged 65 years and older will be concurrently enrolled. Subjects will have screening procedures (physical examination, vital signs, urine pregnancy test for females of childbearing potential), and if eligible, will be enrolled into the study. All subjects will have a urine sample collected as well as blood samples drawn for immunogenicity analysis (OPA and IgG) and safety laboratory analysis at Day 1 (predose) and Month 1 (30 days after vaccination). Subjects will receive VAX-31 or PCV20 on Day 1. Solicited AE will be collected for 7 days after vaccination and unsolicited safety information for 30 days after vaccination, with SAE, NOCI, and MAAE collected up to 6 months after vaccination.

A defined safety review of data (solicited and unsolicited AE and SAE) through 7 days after vaccination of the 64 subjects in Stage 1 will be conducted by an independent Data Monitoring Committee (DMC) before proceeding with Stage 2 of the study.

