## **6.9 Study Vaccine Administration**

On Day 1 before randomization, the medical history, including physical exam (if indicated by updated medical history) and vital signs, and concomitant medications will be collected, females of childbearing potential must have a negative urine pregnancy test, and information updated in the subject file to recheck subject eligibility. Immediately prior to study vaccine administration, the following biological samples will be collected: blood for hematology and chemistry, urine for urinalysis (and if applicable, pregnancy test), and serum for immunogenicity. Once these procedures are performed, study vaccine will be administered. All doses of study vaccine are 0.5 mL in volume and are administered by IM injection with a Sponsor-provided 1 mL syringe and Safety Hypodermic Needle Eclipse 1.5 inch 25 gauge as described above or PCV20 PFS, using universal precautions and sterile technique. All injections will be administered into the deltoid muscle. Injections will be administered by an unblinded staff member delegated by the Investigator.

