## 12. Appendix A: Schedule of Events

Study Event	Screening Visit	Visit 1	Visit 2	Visit 3	Visit 4	Visit 5 to Visit 9	Early Termination
	Screening a (-30 days)	Day 1 a	Day 8 (+3 days)	Day 15 – Phone (+3 days)	Month 1 (±3 days)	Months 2, 3, 4, 5, 6 – Phone (±5 days)	
Informed Consent	X						Refer to Section 7.2 for Procedures
Demographics, Medical History	X	X b					
Concomitant Medications	X	X	X	X	X d	X d	
Physical Exam(s), targeted	X	X b					
Vital Signs	X	X c					
Confirmation of Eligibility	X	X					
Randomization		X					
Study Vaccine Administration		X					
Post-vaccination Observation (at least 30 minutes)		X					
Issue eDiary instructions, Ruler, Thermometer; Conduct Training/Retraining		X					
Review eDiary Data			X				
AE Evaluation (Solicited and/or Unsolicited)		X	X	X	X	X d	
Clinical Labs							
Hematology, Chemistry, Urinalysis		X b			X		
Urine Pregnancy	X b	X b					
Serum for Immunogenicity		X b			X		

- a) Screening and Day 1 Visit are encouraged to be combined; however, subjects may screen for up to 30 days prior to randomizing into the study, and a separate Screening visit may be conducted.
- b) Conduct or collect prior to study vaccination (if indicated by updated medical history or change in health status, as applicable).
- c) Vitals to be taken before and  $\geq 30$  minutes after study vaccine administration.
- d) Only NOCI, MAAE, SAE, and associated concomitant medications collected after Month 1.

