6.5.2. Laboratory Data

- A summary describing pregnancy tests results at Baseline will be presented on the overall population only. The list of Baseline test results to be described is given in *Table 2*.

Table 2 Baseline Laboratory Tests

Panel	Sample	Parameter
Urinalysis	Urine	Pregnancy (urine)

- The lists of laboratory parameters analyzed can be found in *Table 3*. Only the parameters in this table will be presented in the following summaries:
 - The actual value and change from Baseline to Month 1 will be summarized for each clinical laboratory parameter, including hematology, clinical chemistry, and urinalysis. For subjects discontinuing early before Month 1, the value at Early Study Discontinuation will be presented in Listings only.
 - A shift table from Baseline to Month 1 presenting abnormal values for each parameter will also be presented. For subjects discontinuing early before Month 1, the abnormal values at Early Study Discontinuation will be used instead of Month 1.

Clinical laboratory values will be expressed using conventional international system of units (SI). In the event of repeat values, the last non-missing value per study day/time will be used. Clinically significant out-of-range lab results will be reported as adverse events by Investigators. Clinical significance will therefore not be reported in the laboratory outputs.

Table 3 Laboratory Parameters Collected and Summarized in Tables

Panel	Sample	Parameter
Hematology	Blood	Eosinophils (absolute)
Hematology	Blood	Hemoglobin
Hematology	Blood	Neutrophils (absolute)
Hematology	Blood	Platelet count
Hematology	Blood	White blood cell count (absolute)
Chemistry	Serum	Albumin
Chemistry	Serum	Alkaline phosphatase
Chemistry	Serum	Alanine aminotransferase (ALT)
Chemistry	Serum	Aspartate aminotransferase (AST)
Chemistry	Serum	Bicarbonate
Chemistry	Serum	Bilirubin (Total)
Chemistry	Serum	Bilirubin (Direct)
Chemistry	Serum	Blood urea nitrogen (BUN)
Chemistry	Serum	Calcium
Chemistry	Serum	Chloride
Chemistry	Serum	Cholesterol
Chemistry	Serum	Creatinine
Chemistry	Serum	Gamma-glutamyl transferase (GGT)
Chemistry	Serum	Glucose (random)
Chemistry	Serum	Lactate dehydrogenase (LDH)

Chemistry	Serum	Phosphorus
Chemistry	Serum	Potassium
Chemistry	Serum	Protein total
Chemistry	Serum	Sodium
Chemistry	Serum	Triglycerides
Chemistry	Serum	Uric acid
Urinalysis	Urine	Bilirubin
Urinalysis	Urine	Blood
Urinalysis	Urine	Glucose
Urinalysis	Urine	Ketones
Urinalysis	Urine	Leucocyte Esterase

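### SAP 6.2.2 admits Day 1 samples taken after the injection as laboratory and immunogenicity baseline and gives a pre-dose sample no priority

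*SAP*

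**What the plan says.** SAP 6.2.2 has two baseline rules.

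- Laboratory parameters and immunogenicity: "baseline is defined as the assessment collected the closest to the study vaccine administration on Day 1 or prior to study vaccine administration", reaching back up to 30 days. The section then adds: "Laboratory and immunogenicity results from samples collected on Day 1 after the vaccine injection can still be considered as baseline results".
- Vital signs: "baseline is defined as the last non-missing assessment prior to study vaccine administration".

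The protocol places the Day 1 blood, urine and serum before the dose. Section 6.9 states: "Immediately prior to study vaccine administration, the following biological samples will be collected". Footnote b of the Appendix A schedule, attached to the Day 1 laboratory and serum rows, reads: "Conduct or collect prior to study vaccination". The synopsis and protocol section 7.1.2 agree, and SAP 2.1 repeats the pre-vaccination timing.

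For repeated laboratory results, SAP 6.5.2 says: "In the event of repeat values, the last non-missing value per study day/time will be used". The baseline window for the Immunogenicity Evaluable Population (IEP) in SAP 4.1 is the whole of Day 1 or the 30 days before vaccination.

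**The concern.** A baseline should be free of the exposure being studied. The Day 1 part of the laboratory and immunogenicity rule has no pre-dose condition, and its only time limit after the injection is the end of the calendar day. The sentence admitting post-injection samples is not confined to subjects who lack a pre-dose one. The SAP gives no reason for treating these endpoints differently from vital signs.

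If a post-injection value is used, anything the vaccine has already changed by the time of the draw becomes part of the starting value. The exposed outputs are:

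- laboratory change from baseline to Month 1, a secondary endpoint;
- the baseline side of the laboratory shift table, which separates new abnormalities from pre-existing ones;
- the fold ratio, hence GMFR and the 4-fold rise;
- the log10 baseline covariate in the ANCOVA, and likewise in the logistic regression named in SAP 6.2.3.

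The wording is also loose enough for two programmers to derive different baselines for the same subject.

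**Working it through.** No stated figure in the plan depends on this rule, so there is none to reproduce. The check applies the rule to example sample times and then bounds its effect.

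**1. What each rule selects.** Let t be hours from injection. The literal 6.2.2 rule takes the smallest |t|, with post-dose Day 1 values allowed. The strict rule takes the largest t at or before 0. The last column reads the 6.5.2 repeat-value rule per day.

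| Samples available (h) | Literal 6.2.2 | Strict pre-dose | Last value, per day |
|---|---|---|---|
| −1.0 | −1.0 | −1.0 | −1.0 |
| −1.0, +0.5 | **+0.5** | −1.0 | **+0.5** |
| −0.25, +0.5 | −0.25 | −0.25 | **+0.5** |
| −336 (14 × 24), +0.5 | **+0.5** | −336 | **+0.5** |
| +0.5 only | **+0.5** | none | **+0.5** |

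The literal rule prefers a post-dose sample whenever it is nearer in time than the pre-dose one. In the third row the 6.2.2 rule and the per-day reading of 6.5.2 disagree with each other. Only the strict rule protects the pre-dose value throughout, and it leaves the last subject without a baseline.

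**2. Whether another rule catches it.** The IEP window covers all of Day 1, so the programmed out-of-window check in SAP 4.2 need not remove a post-dose Day 1 sample.

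**3. Direction of the error.** Let B be the true pre-dose value, a the acute change present at the draw, and M the Month 1 value. The true change is M − B and the recorded change is M − (B + a), so the error is −a.

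- If the change persists (M = B + a), the true change is a and the recorded change is 0: the effect is hidden.
- If it resolves (M = B), the true change is 0 and the recorded change is −a: an apparent change is created.

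**4. Size, on assumptions.** The documents give neither a rate of post-dose samples nor a size of acute change.

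- Subjects: 0.5% to 2% of 1000 gives 0.005 × 1000 = 5 to 0.02 × 1000 = 20. Each would carry such a baseline for up to 36 laboratory parameters (SAP Table 3: 5 hematology + 21 chemistry + 10 urinalysis).
- Mean change: if a share f of subjects has a post-dose baseline already holding a share g of the Month 1 change, the mean change shrinks by f × g. For f = 1% and g = 5% this is 0.01 × 0.05 = 0.05%. For f = 10% and g = 50% it is 0.10 × 0.50 = 5%. In an arm of 250, those values of f are 2.5 and 25 subjects. This formula covers the persistent case only.

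**5. What does not move.** The percentage with abnormal laboratory values at Month 1 is defined at that visit and needs no baseline. The Month 1 GMT/GMC ANOVA, which protocol 10.7.1 makes the primary model, has treatment group and site as its only terms.

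**The case against.** The strongest reply is that a pre-dose sample will seldom be displaced. Only one Day 1 laboratory and serum collection is scheduled, before the dose, and none at Screening. A draw prompted by a reaction would be unscheduled, and SAP 5.2 keeps unscheduled results in listings unless they are mapped to an analysis visit. The mapping rules it refers to (section 5.5) are not in the public text. A lost tube leaves no pre-dose result to displace. This stands, and it makes a single late-drawn sample the likelier route.

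For that route, the sentence can be read as a sensible fallback: a same-day value may be better than losing the subject. That also stands as a trade-off, but the text does not limit itself to that case.

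There are safeguards too. Clinically significant out-of-range results are reported as adverse events, all laboratory data are listed, and protocol deviations are documented and listed. These make a late draw traceable, but they neither mark the derived baseline nor show whether the tables depend on it.

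Three stronger readings are tempting and not supported:

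- A reader might infer that both secondary laboratory endpoints are compromised. Only change from baseline is; the Month 1 abnormality percentage uses no baseline.
- A reader might infer that the rule always pulls change toward zero and so conceals vaccine effects. Step 3 shows that the direction depends on persistence. A purely transient change would not appear in a comparison of pre-dose with Month 1 values anyway.
- A reader might infer that post-dose values will routinely replace pre-dose ones. The schedule makes that uncommon.

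**Conclusion.** The point holds as a gap in a definition. SAP 6.2.2 permits a post-exposure baseline, can select one over an available pre-dose result, and departs from the protocol's collection timing and from its own vital-signs rule. Few subjects are likely to be affected; 5 to 20 rests entirely on an assumed rate of 0.5% to 2%. Antibody movement within hours should be small, and any effect is probably similar across arms. The main conclusions are not threatened. What remains at risk is the record of individual subjects in the change, shift, fold-rise and ANCOVA outputs. Severity is low: this is a cheap improvement.

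**What to change.** In SAP 6.2.2:

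1. Define laboratory and immunogenicity baseline as the last non-missing sample before vaccination, within the existing 30-day limit.
2. Allow a post-injection Day 1 sample only when the subject has no pre-dose sample, and flag it in the analysis data and listings.
3. Repeat the laboratory change and shift, fold-rise and ANCOVA outputs without the flagged subjects as a sensitivity check.

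In SAP 6.5.2, make the Day 1 repeat-value rule apply to pre-dose values only.

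The cost is a few lines of text and slight extra programming. Because the fallback stays, no subject loses a baseline in the main outputs; flagged subjects drop out only of the sensitivity versions. Sample size, power and significance level are unchanged.

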6.2.3. Adjustments for Covariates

The randomization for Stage 1 will not be stratified.

The randomization for Stage 2 will be stratified by site.

[figure not shown]
Immunogenicity analyses:

- For the Analysis of variance (ANOVA), study site will be included as fixed effect in the model.
- For the Analysis of covariance (ANCOVA) and the logistic regression, study site will be included as fixed effect and the log baseline titer will be included as covariate in the model.

The rationale for including baseline values as a covariate is that prior data have shown vaccine response is correlated with baseline antibody levels.

